#### Participant Recruitment and Screening

Potential participants will be identified for the study by the following methods: 1) University of Kansas Health System healthcare practitioners notify the study team of a potentially eligible participant, and/or 2) Electronic Medical Record (EMR) screening by the study team. A screening of the EMR will be conducted to determine if participants meet preliminary criteria, as outlined in the inclusion/exclusion criteria (i.e., no additional neurologic disease, oxygen-dependent chronic obstructive pulmonary disease, etc.). Potential participants who meet the preliminary criteria will then be approached for interest in participation.

For individuals who wish to participate, a study team member will review the consent form and complete the consent comprehension questions with this individual. If the individual chooses to participate and provides written informed consent, consent will be documented in EPIC O2, physician clearance for participation will be obtained from a KU Physical Medicine and Rehabilitation physician, and the following will occur:

Basic demographic information such as date of birth, age, sex, gender, height, weight, and race/ethnicity will be collected and stored in REDCap®. We will also collect: participant address, contact methods (phone and/or email), and stroke information (i.e., date of stroke, type of stroke, location of stroke, etc.).

Visits 1 and 2 will be performed by trained personnel with experience administering exercise in stroke. Visits will occur  $\geq 2$  hours after meals, and participants will be asked to avoid caffeine for 4-6 hours prior.

Visit 1:

1. The American College of Sports Medicine cardiac risk screen will be completed, as done in STUDY00147598 to provide increased insight into cardiovascular health.
2. Participants will be fitted with a Polar heart rate monitor to continuously monitor heart rate throughout exercise, and a resting blood pressure will be taken.
  - Substep: As shown in the inclusion/exclusion criteria, participants must be able to exercise at 30 watts for 3 minutes on the TBRS to demonstrate their ability to perform the Total Body Recumbent Stepper (TBRS) Submaximal Exercise Test. If inpatient therapists have not previously confirmed or documented the participant's ability to use the TBRS, the participant will be asked to demonstrate an ability to step at 30 watts for 3 minutes on the TBRS. Following successful completion of this task, participants will be asked to rest to allow their heart rate to return to near resting values. If a participant is unable to complete this task, they will be deemed ineligible for the study.
3. Participants will complete the TBRS Submaximal Exercise Test[38] with oversight from a trained study team member, and as performed in protocols STUDY00146161 and STUDY00147598. Participants will be asked to step at a step rate of  $\sim 90$ -100 steps per minute until one of the following occurs: 1) 85% of age-predicted heart rate maximum (HRmax) is reached, 2) All four stages of the test are completed, or 3) Participant requests to stop. Each stage of the test is approximately 3 minutes in duration and consists of increasing resistance. We have previously employed the TBRS Submaximal Exercise Test in subacute stroke with success.[39]
  - As done in STUDY00147598, American College of Sports Medicine Guidelines will be used to guide test termination indications for submaximal exercise testing:
  - Absolute Indications:
    - o Drop in systolic blood pressure of  $>10$  mmHg, despite an increase in workload,
    - o Moderate to severe angina
    - o Central nervous system symptoms (i.e., ataxia, dizziness, or near syncope)
    - o Signs of poor perfusion (cyanosis or pallor)
    - o Any arrhythmia that interferes with normal maintenance of cardiac output during exercise
    - o Technical difficulties with equipment that interferes with testing or participant safety
    - o The individual requests to stop
  - Relative Indications:
    - o Increasing chest pain
    - o Fatigue, shortness of breath, wheezing, leg cramps, or claudication

- Exaggerate hypertensive response (systolic blood pressure  $>250$  mmHg or diastolic blood pressure  $>115$  mmHg)

4. Blood pressure will be taken immediately following completion of the TBRS Submaximal Exercise Test, as done in STUDY00147598, and participants will be asked to subjectively evaluate exercise intensity using the Rating of Perceived Exertion.
5. The participant will rest to allow heart rate and blood pressure to return to near resting values.
6. A HIIT familiarization bout will be performed, as done in STUDY00146161.
  - The familiarization will last for no more than 10-minutes. Participants will perform 1-minute high-intensity intervals at  $\sim 70\%$  peak power output (range: 65-95% peak power output), interspersed with 1-minute active recovery intervals at  $\sim 10\%$  peak power output. An upper heart rate limit of  $85\% \text{ HR}_{\text{max}}$  will be used to align with the upper heart rate limit used in our TBRS Submaximal Exercise Test.
7. Blood pressure will be obtained. To complete the session, the participant's blood pressure must be  $<180/100$  mmHg, and heart rate must be below  $<100$  beats per minute. As such, blood pressure recordings may be repeated as necessary.
8. The heart rate monitor will be removed from the participant.

## Visit 2

1. Participants will be fitted with a Polar heart rate monitor, and resting vitals (heart rate and blood pressure) will be obtained.
2. Participants will perform a 1-minute warm-up at  $\sim 30\%$  peak power output.
3. Participants will perform the HIIT bout:
  - 1-minute high-intensity intervals will be interspersed with 1-minute active recovery intervals for a total of 10 minutes. As used in STUDY00147598, high-intensity intervals will be prescribed at  $\sim 70\%$  peak power output (range: 65-95% peak power output) with a target heart rate range of 75-85%  $\text{HR}_{\text{max}}$  or 60-89% heart rate reserve. The upper heart rate limit of  $85\% \text{ HR}_{\text{max}}$  aligns with the upper heart rate limit used in the TBRS Submaximal Exercise Test. Active recovery intervals will be performed at  $\sim 10\%$  peak power output.
4. Blood pressure will be taken immediately post-HIIT, and participants will perform a  $\sim 1$ -minute cool-down at  $\sim 20\%$  peak power output. Participants will also be asked to subjectively evaluate the HIIT bout using the Rating of Perceived Exertion.
5. Heart rate will be monitored 30minutes to one hour following HIIT completion and blood pressure will be recorded within one hour of conclusion of the study.

6. During the monitoring period, the PACES-8 will be administered to assess exercise acceptability.
7. The heart rate monitor will be removed from the participant.

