**F. Risk/benefit assessment:**

Potential Benefits of Proposed Research

The participant may or may not benefit from this study. Researchers hope that the information gained from this study may be useful in developing increased insight into accessible HIIT modalities for stroke recovery during inpatient rehabilitation.

Potential Risks of Proposed Research

**Exercise:** There are certain risks and discomforts that may be associated with exercise such as temporary shortness of breath, muscle fatigue, sweating, and physical discomfort. It is extremely unlikely, but there is always the risk of having a serious heart problem, such as developing an abnormal rhythm, heart attack, or having another stroke during exercise. To protect and minimize risks during exercises, the study team will monitor heart rate and blood pressure during all exercise procedures and obtain physician clearance prior to exercise engagement. If a participant would report chest discomfort, dizziness or any other problems, exercise will be discontinued. We have successfully studied individuals with stroke during the TBRS submaximal exercise test (HSC#2173) during inpatient stroke rehabilitation without serious adverse events. We have also successfully implemented a single bout of low-volume, short-interval HIIT in chronic stroke (STUDY00146161). Our laboratory team is well equipped and trained to execute this study.

**Blood pressure:** A participant may experience mild discomfort in the upper extremity when assessing blood pressure due to cuff inflation. Should this occur, the cuff can be deflated.

**Possibility of unknown risks:** There may be other side effects or risks that are not yet known. The study team will work to minimize any discomfort associated with the aforementioned procedures.

**G. Location where study will be performed:** This study will take place at Kansas University Medical Center Inpatient Rehabilitation. Address: The Second Floor of [name]

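### Section II.E makes increasing chest pain only a relative reason to stop the Visit 1 submaximal test, while section II.F says exercise stops when chest discomfort is reported

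*Protocol*

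**What the plan says.** Protocol section II.E, Visit 1 step 3, describes the submaximal stepper test. Its stop list is introduced by the statement that "American College of Sports Medicine Guidelines will be used to guide test termination indications for submaximal exercise testing", and is divided into absolute and relative indications.

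- Absolute, among others: "Moderate to severe angina"; "Central nervous system symptoms (i.e., ataxia, dizziness, or near syncope"; and a request by the participant to stop.
- Relative: "Increasing chest pain"; a group made up of fatigue, shortness of breath, wheezing, leg cramps and claudication; and an exaggerated blood pressure response.

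On the course of the test, the same step says: "Each stage of the test is approximately 3 minutes in duration and consists of increasing resistance".

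Protocol section II.F, in the exercise paragraph under potential risks, describes the protections. It says that "the study team will monitor heart rate and blood pressure during all exercise procedures", and then: "If a participant would report chest discomfort, dizziness or any other problems, exercise will be discontinued".

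**The concern.** The two sections treat the same report differently. A participant whose chest pain is increasing but short of moderate angina, and who does not ask to stop, meets a relative indication in II.E. Under II.F the same report ends the exercise. Because resistance rises from stage to stage, continuing past a stage boundary means a higher workload.

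What is at stake is patient safety and consistency. The participants are inpatients with subacute stroke, and Aim 1 defines safety as the absence of study-related cardiac or serious adverse events. II.F offers stopping on chest discomfort as one of the measures that limit the exercise risk, so the list for the test should require the same action.

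**Working it through.** No sample size, power or event figure is involved, so nothing is computed. The check sets the two sections side by side.

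1. **Scope.** The II.E list is written for submaximal testing at Visit 1. The II.F sentence comes straight after a statement of safeguards for all exercise procedures, so it also covers the Visit 1 test. Both texts apply to it.

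2. **Required action, by symptom.**

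| Report during the Visit 1 test | II.E | II.F |
|---|---|---|
| Moderate to severe angina | Absolute: stop | Stop |
| Increasing chest pain below that level | Relative: judgment | Stop |
| Dizziness | Absolute: stop | Stop |
| Participant asks to stop | Absolute: stop | Not addressed separately |
| Fatigue, shortness of breath, wheezing, leg cramps | Relative: judgment | Stop only if read as falling under the catch-all phrase |

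3. **Where they differ.** II.F names two symptoms and then adds a catch-all. Dizziness agrees across the sections. Chest discomfort agrees only from moderate angina upward. The last row depends on how widely the catch-all is read. The same II.F paragraph lists temporary shortness of breath and muscle fatigue among the ordinary discomforts of exercise, which argues against reading it to stop exercise for those two.

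4. **Meaning of relative.** The protocol does not define the term. That it leaves stopping to judgment is inferred from the contrast with the absolute list. On that reading a relative indication permits stopping and does not require it.

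5. **Precedence.** No section says that II.F overrides the II.E list, or the reverse.

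6. **The other exercise bouts.** The steps in II.E for the familiarization bout and the Visit 2 interval bout give power and heart rate limits but no list of symptoms for stopping. The II.F sentence is the only symptom-based stop rule there. This bears on which section should be edited.

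**The case against.** The strongest reply is that no event makes it impossible to comply with both sections. A relative indication allows stopping and II.F says to stop, so staff who stop satisfy both. II.F is protocol text as binding as II.E, and it does tell staff what to do once chest discomfort is reported. The II.E list is said only to guide termination; it never orders anyone to continue. This stands, and it rules out two stronger readings. A reader might infer that the protocol directs staff to exercise patients through chest pain, or that staff will work from the II.E list and disregard II.F. The documents say neither.

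A second reply is that the risk is already limited: ongoing unstable angina is excluded, physician clearance is required, a trained team member oversees the test, and a request to stop ends it. These lower the chance of the situation arising or persisting. They do not settle which stop rule applies to chest pain below moderate angina.

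A third reply is that II.F may be summary risk language, so that aligning it with the II.E list would repair the mismatch equally well. It would restore consistency. But if II.F were cut back to the II.E list, the familiarization and Visit 2 bouts would lose the only unconditional symptom rule that covers them.

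Finally, II.E attributes its list to a guideline that is not available here. The list cannot be called deficient as a guideline list, and this point does not do so. It says only that the protocol promises more in II.F than its own list requires.

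**Conclusion.** The mismatch is real and narrow. For chest pain below moderate angina during the Visit 1 submaximal test, II.E allows discretion where II.F gives stopping as the protection, and the protocol does not say that II.F governs. The conclusion assumes that a relative indication leaves stopping to judgment, and that II.F covers the Visit 1 test, as its reference to all exercise procedures indicates.

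It is a minor safety harmonization. A reader might be tempted to turn the stage structure ("All four stages of the test are completed", with each stage of about 3 minutes) into minutes at risk. That would only restate how long the test lasts. The protocol gives no rate of chest discomfort, and nothing in it shows that staff would set II.F aside. Nor should one tally agreement over only the two symptoms that II.F names, since that drops its catch-all. No result for Aim 1 or Aim 2 and no analysis figure changes.

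**What to change.** In section II.E, Visit 1 step 3, delete increasing chest pain from the relative indications and add *any chest pain or discomfort* to the absolute indications. Keep the II.F sentence as written. Fatigue, temporary shortness of breath and similar expected effects of exercise can stay relative, although the II.F catch-all could be read to include them.

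The cost is two wording edits in one list and a short staff briefing. A few submaximal tests may end early, and on this item the protocol becomes stricter than the guideline-based list it draws on. There is no new procedure and no change to the sample size or the analysis.

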We will recruit up to 25 patients admitted to The University of Kansas Acute Inpatient Rehabilitation Unit with subacute stroke, age 18-85 years, to perform a single bout of short-interval (60 seconds), low-volume (10 minutes) HIIT on the TBRS, in line with the protocol used in STUDY00146161 (NCT04673994).

**Aim 1: Explore the safety of short-interval; low volume HIIT in stroke.** Safety will be defined as the presence of no study-related cardiac or serious adverse events.[14] We hypothesize that low-volume, short-

interval, TBRS HIIT will be safe in individuals with subacute stroke while admitted to inpatient rehabilitation during HIIT (**H1a**) and within the 30 minutes following HIIT cessation (**H1b**).

**Aim 2: Explore the feasibility of short-interval, low-volume HIIT in stroke.** Feasibility will be assessed by adherence to the exercise session, attainment of target heart rates, and acceptability of the exercise. At least 75% of participants will complete the entire 10-minute HIIT bout, (**H2a**) and  $\geq 75\%$  of participants will reach target heart rates (75%-85% max HR) during  $\geq 75\%$  of the high-intensity intervals (**H2b**). To examine acceptability, the valid and reliable 8-item Physical Activity Enjoyment Scale (PACES-8) will be used, where higher scores indicate greater exercise enjoyment (**H2c**)[15-19].

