**C. Sample size, statistical methods, and power calculation**

1. We plan to recruit a sample of up to 25 participants. This sample size aligns with other feasibility trials examining HIIT in stroke.[14, 34]
2. Blinding: No blinding will be used.
3. Analytic and statistical methods to be used: Descriptive statistics will be used to report adverse events, participants who completed the entire HIIT bout, target heart rates achieved, and PACES-8 scores.

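### The reserve-scale heart rate target at Visit 2 runs above the 85% HRmax limit in the next sentence and does not match the range that H2b scores

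*Protocol*

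**What the plan says.** All references are to the protocol.

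- **Section II.E, Visit 2 step 3.** High-intensity intervals are prescribed by power output "with a target heart rate range of 75-85"% HRmax. A second scale is then offered, and an upper limit follows at once: "or 60-89% heart rate reserve. The upper heart rate limit of" 85% HRmax. The reason given for that limit is that it "aligns with the upper heart rate limit used in the TBRS Submaximal Exercise Test".
- **Section II.E, Visit 1 step 3.** The submaximal test stops at "85% of age-predicted heart rate maximum". No prediction formula is named and no maximal test is described.
- **Section II.E, Visit 1 step 6.** For the familiarization bout, the 85% HRmax limit "will be used to align with the upper heart rate limit used in our TBRS Submaximal Exercise Test". No target band is set for that bout on either scale.
- **Section II.E, Visit 2 step 1.** "resting vitals (heart rate and blood pressure) will be obtained", so the resting rate needed for a reserve calculation is collected.
- **Sections I.A and II.A, Aim 2.** H2b expects that at least 75% "of participants will reach target heart rates (75%-85% max HR) during" at least 75% of the high-intensity intervals. No reserve range is mentioned.
- **Sections II.C (item 3) and V.A.** The descriptive analysis covers "target heart rates achieved, and PACES-8 scores", without saying on which scale.

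Heart rate reserve appears only in Visit 2 step 3. No rule says when it replaces the HRmax range.

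**The concern.** Two things do not fit together. First, the two Visit 2 targets are joined by *or*, yet they are not interchangeable, and the reserve band runs past a limit stated in the very next sentence. Staff supervising inpatients with subacute stroke are left without one clear instruction. Second, the target that staff may work to is wider than the range that H2b scores.

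The second matter bears on Aim 2 because the H2b count is coarse. One-minute intervals alternating over 10 minutes give five high-intensity intervals. Since 0.75 x 5 = 3.75, a participant needs four of the five, and two intervals scored as outside the range are enough to fail. With 25 participants, 0.75 x 25 = 18.75, so 19 must succeed.

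**Working it through.** **Inputs.** From the protocol: the reserve band of 60-89%, the HRmax range of 75-85%, the limit of 85% HRmax, and ages 18-85. Assumed: both scales use the same HRmax (M), M = 220 - age for the illustrations, and resting heart rate (R) of 60-90 bpm. The protocol gives no figure of its own to reproduce here.

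**Definition.** Heart rate at reserve fraction f is R + f(M - R).

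**1. Top of the reserve band against the limit.**
0.89M + 0.11R - 0.85M = 0.04M + 0.11R. This is positive for any M and R, so the result needs no prediction formula.
- Smallest value under the assumptions (age 85, R = 60, M = 135): 5.40 + 6.60 = 12.0 bpm.
- Largest (age 18, R = 90, M = 202): 8.08 + 9.90 = 17.98 bpm.

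As a sensitivity check, R was widened to 40-100 bpm and three formulas were tried. The excess is 9.8 to 19.1 bpm with 220 - age, 10.3 to 18.8 with 208 - 0.7 x age, and 8.6 to 17.1 with 164 - 0.7 x age.

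**2. When the whole reserve band is above the limit.**
0.60M + 0.40R > 0.85M, that is R > 0.625M. At R = 90 this means M < 144, or age over 76 with 220 - age.

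**3. Bottom of the reserve band against the H2b floor.**
0.60M + 0.40R - 0.75M = 0.40R - 0.15M, which is negative when R < 0.375M. The largest gap under the assumptions is at age 18, R = 60: 24.0 - 30.3 = -6.3 bpm. At R = 60 the gap exists only below age 60 (220 - 60/0.375). At R = 80 the cut-off is age 6.7, so within the trial's age range it does not occur at R = 80 or more.

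**Examples (220 - age, bpm).**

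| Age, R | M | 75-85% HRmax | 60-89% reserve | Top minus 85% HRmax |
|---|---|---|---|---|
| 18, 60 | 202 | 151.5-171.7 | 145.2-186.4 | 14.7 |
| 40, 60 | 180 | 135.0-153.0 | 132.0-166.8 | 13.8 |
| 65, 70 | 155 | 116.25-131.75 | 121.0-145.65 | 13.9 |
| 80, 90 | 140 | 105.0-119.0 | 120.0-134.5 | 15.5 |

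**4. The two ways to read Visit 2 step 3.**
- *The limit does not cap the reserve scale*, for instance because the sentence only explains the 85 in the first range. The written target then permits heart rates above the stated limit, and an interval can be on target while above the H2b range.
- *The limit caps both scales.* The 89% bound then has no function. Where R > 0.625M the reserve option is empty: in the last row, the band starts at 120.0 against a limit of 119.0.

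Under either reading, where R < 0.375M, an interval whose heart rate stays between 60% reserve and 75% HRmax meets the Visit 2 target but never enters the H2b range.

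**The case against.** The strongest defence is that the 85% limit simply governs. The protocol speaks of *the* upper limit as one already known, and applies it in the familiarization bout. On that reading nobody is directed above 85% HRmax, and the mismatch with H2b shrinks to the floor gap of at most 6.3 bpm, absent at resting rates of 80 or more. This is a fair reading, and it means that the 12 to 18 bpm range has practical force only if the limit does not cap the reserve scale. But the text does not say that it does, and the reading leaves a bound with no use and, for some participants, an option with no content.

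A second defence is that H2b names one clear range, in the same words in both places. That stands: H2b itself is not ambiguous, and nothing says that it would be scored on reserve.

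Four stronger readings are tempting but unsupported:
- *Every interval that ends above 85% HRmax fails H2b.* H2b speaks of reaching the range. A heart rate that climbs through 75-85% and ends above it fails if the peak is scored, may fail if the mean is, and passes if any value counts. The protocol does not state the rule, which may properly be left to the SAP.
- *The familiarization bout contradicts Visit 2.* It sets only an upper limit and no target band, so there is nothing for a reserve alternative to attach to. It only shows the same limit being applied elsewhere.
- *Delivered exercise will exceed the limit.* Intervals are prescribed by power output with heart rate alongside, so this cannot be shown from the document.
- *A reserve floor above 75% HRmax is a further mismatch.* With *or*, an interval within 75-85% HRmax is on target even if it is below 60% reserve.

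Finally, the result needs one HRmax on both scales. The prescription is attributed to another study whose protocol is not at hand, but this protocol names only an age-predicted maximum, so a common HRmax is the natural reading.

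**Conclusion.** The point holds as an inconsistency of wording. Given a common HRmax, the top of the reserve band is above the stated limit for every participant. The size is 12 to 18 bpm under 220 - age, ages 18-85 and resting rates of 60-90 bpm, and the whole band is above the limit where the resting rate exceeds 62.5% of HRmax. Neither reading of the limit makes the Visit 2 target, the limit and H2b agree. The sign of the excess does not depend on the prediction formula; the bpm figures do.

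The consequence for Aim 2 is a possibility, not a demonstrated bias. The effect on the H2b proportion cannot be computed, because it depends on the unstated scoring rule and on heart rates not yet observed. In a single-group descriptive study of up to 25 people with a fixed H2b range, the severity is minor to should-fix.

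**What to change.** Reconcile three things so that they agree: the target in Section II.E, Visit 2 step 3; the upper heart rate limit stated there; and the H2b range in Sections I.A and II.A. In doing so, make explicit whether the limit applies to the reserve scale. Which range or limit is right is for the sponsor to decide.

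If a reserve-based target is kept, report attainment on that scale separately from H2b, and say so in Section II.C (item 3) and Section V.A.

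The cost is a wording amendment and, if both scales stay, slightly more descriptive reporting. If only one scale is kept, staff lose the choice between them. No new data are needed: heart rate is monitored during the bout and the resting rate is already taken at Visit 2.
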